6.2. Study Drug Administration

Patients will be instructed to take one capsule/tablet from each bottle by mouth daily, at approximately the same time each day, on an empty stomach (no food or drink besides clear liquids for approximately 2 hours before and 1 hour after study drug administration), for a total of 2 capsules and 2 tablets each day as shown in Table 6.

For subjects participating in the PK/PD sub-study, study drug should be administered approximately 24 hours prior to their Week 12 visit.

Dose Group	TERN-501 Capsules	TERN-501 Placebo to Match	TERN-101 Tablets	TERN-101 Placebo to Match
Placebo QD	Not applicable	Two placebo capsules	Not applicable	Two placebo tablets
TERN-501 1 mg QD	One 1 mg capsule	One placebo capsule	Not applicable	Two placebo tablets
TERN-501 3 mg QD	One 3 mg capsule	One placebo capsule	Not applicable	Two placebo tablets
TERN-501 6 mg QD	Two 3 mg capsules	Not applicable	Not applicable	Two placebo tablets
TERN-501 3 mg QD + TERN-101 10 mg QD	One 3 mg capsule	One placebo capsule	Two 5 mg tablets	Not applicable
TERN-501 6 mg QD + TERN-101 10 mg QD	Two 3 mg capsules	Not applicable	Two 5 mg tablets	Not applicable
TERN-101 10 mg QD	Not applicable	Two placebo capsules	Two 5 mg tablets	Not applicable

Table 6Study Drug by Dose Group

Abbreviations: QD = once a day

6.3. Preparation/Handling/Storage/Dispensing/Accountability

The Investigator or designee must provide acknowledgement of receipt of each shipment of study drug including appropriate temperature conditions have been maintained during transit for all study drug received and any discrepancies are reported and resolved before use of the study drug.

Only patients enrolled in the study may receive study drug and only authorized site staff may supply or administer study drug. All study drugs must be stored in a secure, environmentally controlled, and monitored (manual or automated) area in accordance with the labeled storage conditions with access limited to the Investigator and authorized site staff.

The Investigator, institution, or the head of the medical institution (where applicable) is responsible for study drug accountability, reconciliation, and record maintenance (ie, receipt, reconciliation, and final disposition records).

Further guidance and information for the final disposition of unused study drugs are provided in the Pharmacy Manual.

6.4. Measures to Minimize Bias: Randomization and Blinding

Patients will be randomized to 1 of 3 dose levels TERN-501 monotherapy, 1 of 2 dose levels TERN-501+TERN-101, 10mg TERN-101 monotherapy, or placebo using an Interactive Web Response System (IWRS). Before the study is initiated, the log-in information and directions for the IWRS will be provided to each site.

Approximately 140 patients will be randomized equally into one of the 7 treatment groups to receive once daily orally administered TERN-501 1 mg (n=20), TERN-501 3 mg (n=20), TERN-501 6 mg (n=20), TERN-501 3 mg+TERN-101 10 mg (n=20), TERN-501 6 mg+TERN-101 10 mg (n=20), TERN-101 10 mg (n=20), or matching placebo (n=20).

All personnel directly involved in the conduct of the study (i.e., Investigators, patients, all study personnel, Medical Monitor, and the Sponsor) will remain blinded to each patient's assigned dose group throughout the course of the study. Individuals in IP packaging and labeling who have Unblinded Inventory Manager role in the IXRS system for study drug inventory management will remain unblinded. Individuals at the PK bioanalytical laboratory will remain unblinded to facilitate sample processing, as placebo samples will not be analyzed for PK. Study drug will be dispensed at the study visits as summarized in Schedule of Activities. Returned study drug should not be re-dispensed to patients.

6.4.1. Unblinding

Treatment assignment may be unblinded if knowing the patient's treatment assignment would affect immediate medical management of the patient. The IWRS will be programmed with blindbreaking instructions. In case of an emergency, the Investigator has the sole responsibility for determining if unblinding of a patient's intervention assignment is warranted. Patient safety must always be the first consideration in making such a determination. If the Investigator decides that unblinding is warranted, the Investigator should make every effort to contact the Medical Monitor/Sponsor prior to unblinding a patient's intervention assignment unless this could delay emergency treatment of the patient. If a patient's intervention assignment is unblinded, the Sponsor must be notified within 24 hours after breaking the blind. The date and reason that the blind was broken must be recorded in the source documentation and case report form (CRF), as applicable.

Any unblinding of Sponsor personnel for expedited reporting of suspected unexpected serious adverse reactions (SUSARs) or other reasons will be addressed in a separate plan.

6.4.2. Patient Enrollment and Study Drug Assignment

It is the responsibility of the Investigator to ensure that patient eligibility is confirmed prior to randomization. Documentation of the personally signed and dated informed consent of each patient, using the study specific ICF, is required before initiating the Screening Period.

After written informed consent has been obtained, the patient's identification number will be obtained from the IWRS. Once eligibility to participate has been established, the randomized treatment assignment will be obtained from the IWRS.

6.5. Study Drug Compliance

Patients will be dispensed study during their study visits and will self-administer study drug at home. Compliance will be assessed by direct questioning and counting returned capsules/tablets during the study visits and documented in the source documents and/or electronic case report form (eCRF). Deviation(s) from the prescribed dosage regimen should be recorded in the eCRF.

If a patient is required to be quarantined due to active infection of Coronavirus Disease 2019 (COVID-19) or exposure to COVID-19 or is otherwise unable to visit the site due to COVID-19, study drug may be mailed to the patient or made available via another appropriate mechanism (ie, curbside pickup, etc.).

Patients will be asked to maintain records of self-administered drug on non-study visit days. A record of the number of study drug capsules/tablets dispensed to and taken by each patient must be maintained and reconciled with study drug and compliance records at the site. Study drug start and stop dates, including dates for delays will also be recorded in the eCRF.

6.6. Concomitant Therapy

Any medication or vaccine (including over-the-counter or prescription medicines, vitamins, and/or herbal supplements) that the patient is receiving at the time of randomization or receives during the study must be recorded at each study visit along with:

- Reason for use
- Dates of administration including start and end dates
- Dosage information including dose and frequency

Thyroid hormone replacement therapy during the study treatment:

• If determined necessary by Investigator, in consultation with the Medical Monitor, dose adjustment (dose increase or decrease, or discontinuation) of thyroid hormone replacement therapy with levothyroxine is allowed once after at least 6 weeks of study drug administration. See Section 8.1.8 for more information on thyroid axis safety monitoring

Medications prohibited for use through the end of study:

- Medications or therapies that may interfere with thyroid function (except in patients who were on a stable dose of thyroid hormone replacement therapy with levothyroxine for primary hypothyroidism prior to study entry), including but not limited to initiation of thyroid hormone replacement therapy, methimazole, propylthiouracil, tyrosine kinase inhibitors, lithium, iodide, and propranolol; patients who require such medications or therapies must discontinue study drug (See Section 7.1.2.)
- Medications specifically used for weight loss
- Medications with potential impact on NASH outcome, including resmetirom or other investigational THR- β agonists, obticholic acid or other investigational FXR agonists, pioglitazone or other PPAR γ agonists, or high-dose vitamin E (> 400 IU/day)

Medications potentially impacting steatohepatitis, including but not limited to systemic corticosteroids (prednisone equivalent of > 10 mg/day for > 2 weeks), amiodarone, tamoxifen and methotrexate. Use of systemic corticosteroids for ≤ 2 weeks within 3 months prior to randomization and through the end of the study is allowed

Medications discouraged for initiation, discontinuation, or dose adjustment through the end of study, but allowed if deemed necessary for clinical management at Investigator's discretion:

- Vitamin $E \le 400 \text{ IU/day}$
- Metformin, GLP-1 analogues, DPP-4 inhibitors, SGLT2 inhibitors, and other diabetic drugs
- Insulin with > 30% dose adjustment (Note: $\le 30\%$ dose adjustment is allowed)
- Statins, PCSK9 inhibitors, or other lipid modifying medications
- Hormonal contraceptives

Medications prohibited for use through the last dose of treatment:

There is potential for TERN-501 absorption to be increased or decreased by co-administered drugs that are intestinal P-gp and BCRP inhibitors or inducers, respectively, based on in vitro data. As such, strong P-gp and/or BCRP inhibitors or inducers are prohibited from this study.

There is potential for CYP3A4 inhibitors or inducers to increase or decrease the exposure of TERN-101, respectively. As such, strong CYP3A4 inhibitors or inducers are prohibited from this study.

A noncomprehensive list of known strong CYP3A inducers and inhibitors, P-gp inhibitors and inducers, and BCRP inhibitors is provided below:

- Potent CYP3A inhibitors prohibited on study include but are not limited to: boceprevir, cobicistat, ritonavir, grapefruit juice, itraconazole, ketoconazole, osaconazole, telaprevir, telithromycin, troleandomycin, voriconazole, clarithromycin, idelalisib, nefazodone, and nelfinavir
- P-gp inhibitors prohibited on study include but are not limited to: amiodarone, carvedilol, clarithromycin, cyclosporine, dronedarone, itraconazole, lapatinib, propafenone, quinidine, ranolazine, ritonavir, and verapamil
- BCRP inhibitors prohibited on study include but are not limited to: curcumin, cyclosporine, eltrombopag
- Potent CYP3A and/or P-gp inducers prohibited on study include but are not limited to: apalutamide, carbamazepine, enzalutamide, fosphenytoin, mitotane, phenytoin, rifampin, and St. John's wort

Patients who require initiation of strong CYP3A and/or P-gp inducers or strong CYP3A, P-gp, and/or BCRP inhibitors during the study should discontinue study drug (Section 7.1.2.). For patients who subsequently discontinue prohibited medications, study drug administration may not be resumed unless agreed by the Medical Monitor. Patients who do not resume study drug will continue in the study to be evaluated at the remaining visits through the Follow-Up visit.

Medications discouraged for use through the last dose of treatment:

Moderate CYP3A inhibitor use is discouraged during study participation. Management of patients who initiate moderate CYP3A4 inhibitors during the course of study treatment should be discussed with the Medical Monitor.

A noncomprehensive list for known moderate CYP3A4 inhibitors is provided below:

• Moderate CYP3A4 inhibitors discouraged on study include but are not limited to: aprepitant, ciprofloxacin, conivaptan, crizotinib, cyclosporine, diltiazem, dronedarone, erythromycin, fluconazole, fluvoxamine, imatinib, and verapamil

The Medical Monitor should be contacted if there are any questions regarding concomitant therapy. Any dose adjustments that may be required during study participation should be discussed with the Medical Monitor.

6.7. Dose Modifications

Dose modifications of study drug are not permitted.

6.8. **Dose Interruptions**

On all non-study visit days, patients will self-administer the study drug orally once daily. If a patient forgets to self-administer study drug at their usual time on a given day, the dose can be taken on the same day when the patient remembers, with the exception below:

• For patients participating in the PK/PD sub-study, drug must be self-administered in the morning approximately 24 hours before their Week 12 visit. If not, the Week 12 PK/PD sub-study visit should be re-scheduled for the following day.

If a patient forgets to self-administer study drug on a given day, it will be designated a missed dose. Dosing may continue orally once daily according to the protocol schedule after a missed dose.

If study drug is discontinued or suspended for safety reasons considered related to study drug, dosing should not be resumed without consultation with the Medical Monitor. Information on stopping study drug for patients due to safety/other reasons is detailed in Section 7.

6.8.1. Dose Interruptions due to COVID-19

If a patient requires home quarantine due to SARS-CoV-2 infection or exposure, or due to COVID-19 symptoms, the patient may continue study drug provided that appropriate safety follow-up is possible and that hospitalization is not required. Home health care visits may be made available to continue study assessments in the patient's home where feasible, and/or remote visits via telephone, telemedicine, or other appropriate virtual communication may be substituted for a visit to the site. Sites should discuss the mechanism for safety follow-up with the Medical Monitor. For additional details for study drug dispensation, please see Section 6.5.

If a patient has symptoms of COVID-19 requiring hospitalization, study drug must be discontinued during hospitalization. A case-by-case assessment of whether to resume study drug can be done upon discharge. Dosing should not be resumed without consultation with the

CONFIDENTIAL

Medical Monitor. The patient should be encouraged to remain in the study to be evaluated at the remaining visits through the Follow-Up visit.

6.9. Intervention after the End of the Study

No further interventions are planned after the end of the study.

7. Discontinuation of Study, Study Drug and Patient Discontinuation or Withdrawal

7.1. Study and Study Drug Stopping Criteria

7.1.1. Study Stopping Criteria

Blinded safety review including, but not limited to, laboratory values, vital signs, ECGs, and AEs will be conducted regularly throughout the study and will assess whether any of the following criteria are met:

- One patient experiences a Grade V CTCAE considered related to study medication by the Investigator, or
- Two patients experience the same Grade IV CTCAE considered related to study medication by the Investigator, or
- Three patients experience the same Grade III CTCAE considered related to study medication by the Investigator

Note: Causality of AEs will be determined by the Investigator based on the 4-category system specified in Appendix 6.

In the event that study enrollment and/or dosing is stopped due to one or more of the criteria specified above, the causality of these adverse events will be further investigated by an Independent Medical Monitor (IMM); if adverse events are deemed to be unrelated to study drug (i.e., TERN-501, TERN-101, or TERN-501+TERN-101) by the IMM, then enrollment and/or dosing may resume.

The Sponsor may temporarily or permanently stop the study at any time for safety concerns.

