7.1.2. Discontinuation of Study Drug

Study drug must be discontinued for an individual patient in the following instances:

- If an AE of Grade 3 or above based on National Cancer Institute (NCI) Common Terminology Criteria for Adverse Events (CTCAE) 5.0 occurs and is considered related to study drug as judged by the Investigator per the guidance in Appendix 6.
- Development of TSH level outside the normal range (confirmed by repeat testing) that is determined to be clinically significant or warrants initiation of new medications or therapies to treat thyroid dysfunction of signs of hyper/hypothyroidism. (Note: Dose adjustment of thyroid hormone replacement therapy with levothyroxine without discontinuing study drug may be allowed once after at least 6 weeks of study drug administration at Investigator's discretion upon consultation with Medical Monitor as referenced in Section 6.6).
- Necessary use of nonpermitted concomitant drug (ie. CYP3A4/P-gp/BCRP strong inhibitor/inducer) as referenced in Section 6.6.

Protocol TERNCB-2002 Terns, Inc.

- Symptoms of COVID-19 requiring hospitalization.
- Change in status that, in the judgement of the Investigator compromises the patient's ability to continue treatment or is not considered to be in the patient's best interest.
- Patient request to discontinue study drug for any reason.
- Pregnancy during the study (refer to Appendix 7).
- Sponsor discretion.
- Discontinuation of the study at the request of the Sponsor, a regulatory agency, or Institutional Review Board (IRB)/Independent Ethics Committee (IEC).

Study drug may be discontinued upon confirmation by repeat testing for an individual patient in the following instances at the discretion of the Investigator, and the Medical Monitor should be informed if any of the following occurs:

- If one of the following laboratory abnormalities is confirmed by repeat testing, considered related to the study drug and does not have alternative etiology (repeat test should be performed within 48-72 hours once initial abnormality is detected):
 - $\circ \quad \text{ALT or AST} > 8 \times \text{ULN}$
 - \circ ALT or AST > 5 × ULN for more than 1 week during study drug administration
 - ALT or $AST > 2 \times Baseline$ with the appearance of fatigue, nausea, vomiting, right upper quadrant pain or tenderness, fever, rash, and/or eosinophilia (> 5%)

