7.3. Interim Analyses and Data Monitoring

No interim analysis or data monitoring committees are planned for this study.

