8.2.1. Overall Summary of Adverse Events

An overall summary of TEAEs will be presented by treatment group. The number and percentage of patients who experience at least one of the following:

- Any TEAE, All CTCAE grades
- Grade 3 or higher TEAE
- Serious TEAE
- TEAE leading to death
- Treatment-related TEAE, All CTCAE grades
- Treatment-related Grade 3 or higher TEAE
- Treatment-related serious TEAE
- TEAE leading to study drug interruption
- TEAE leading to study drug discontinuation
- TEAE leading to discontinuation from the study

CONFIDENTIAL

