8.2.2. Patient Incidence of Adverse Events

6.2.2. I dient incluence of Adverse Events

Summaries will be displayed by SOC and PT and will be ordered by descending order of group 7 incidence of system organ class and preferred term within each system organ class. Summaries of the following types will be presented:

- Patient incidence of TEAEs by MedDRA SOC and PT.
- Patient incidence of TEAEs leading to study drug discontinuation by MedDRA SOC and PT. This is a subset of the AEs where Action Taken with Study Drug is checked as "Drug Withdrawn."
- Patient incidence of TEAEs leading to study drug interruption by MedDRA SOC and PT. This is a subset of the AEs where Action Taken with Study Drug is checked as "Drug Interrupted."
- Patient incidence of TEAEs leading to study discontinuation by MedDRA SOC and PT (subset of the AEs where Reason for Discontinuation on the End of Study CRF is "Adverse Event").
- Patient incidence of TEAE leading to death by MedDRA SOC and PT.
- Patient incidence of TEAEs by MedDRA SOC, PT, and highest severity (CTCAE grade). At each level of patient summarization, a patient is classified according to the highest severity if the patient reported 1 or more events. AEs with missing severity (CTCAE grade) will be considered Grade 3 (severe) for this summary.
- Patient incidence of CTCAE Grade 3 or higher TEAEs by MedDRA SOC and PT. At each level of patient summarization, a patient is classified according to the highest severity if the patient reported 1 or more events. AEs with missing severity (CTCAE grade) will be considered Grade 3 (severe) for this summary.
- Patient incidence of treatment-related TEAEs by MedDRA SOC and PT. Related AEs
 are those with relationships reported as "Related" or "Possibly Related". At each level
 of patient summarization, a patient is classified according to the closest relationship to
 study drug if the patient reported 1 or more events. AEs with a missing relationship
 will be considered related for this summary.
- Patient incidence of treatment-related CTCAE Grade 3 or higher TEAEs by MedDRA SOC and PT. At each level of patient summarization, a patient is classified according

CONFIDENTIAL

to the highest severity if the patient reported 1 or more events. AEs with missing severity (CTCAE grade) will be considered Grade 3 (severe) for this summary. AEs with a missing relationship will be considered related for this summary.

• Patient incidence of serious TEAEs by MedDRA SOC and PT.

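### As worded, the study stopping criteria are not met by two Grade III cases plus one Grade IV case of the same related event, although three Grade III cases would meet them

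*Protocol*

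**What the plan says.** Protocol section 7.1.1 (Study Stopping Criteria) provides for a regular blinded safety review that "will assess whether any of the following criteria are met". There are three criteria, joined by *or*, each limited to events the investigator considers related to study medication:

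- "One patient experiences a Grade V CTCAE"
- "Two patients experience the same Grade IV CTCAE"
- "Three patients experience the same Grade III CTCAE"

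If enrolment and/or dosing is stopped under one of these criteria, an Independent Medical Monitor examines causality, and the study may resume if the events are judged unrelated. The same section lets the sponsor stop the study at any time for safety concerns.

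Other places use cumulative wording. The rule for individual patients in Protocol section 7.1.2 begins "If an AE of Grade 3 or above based on National Cancer Institute". SAP section 8.2.1 lists "Treatment-related Grade 3 or higher TEAE", and SAP section 8.2.2 lists "Patient incidence of CTCAE Grade 3 or higher TEAEs by MedDRA SOC and PT". SAP section 7.3 states: "No interim analysis or data monitoring committees are planned for this study".

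**The concern.** A safety trigger should never become harder to meet as events become more severe. The three lines of section 7.1.1 each name a single grade, with no rule for adding across grades. A Grade IV case can therefore fall outside the Grade III count while being too few to meet the Grade IV line.

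These criteria are the plan's only numeric study-level trigger for pausing enrolment or dosing. They are also the only written route to the Independent Medical Monitor's causality review, which is described as following a stop under these criteria. With no data monitoring committee and a blinded safety review, two careful readers could look at the same tallies and disagree on whether the trigger has been met.

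**Working it through.** The documents give no operating characteristics for this rule, so there is no stated figure to reproduce. The check is an enumeration.

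**Inputs.** Thresholds of 1 (Grade V), 2 (Grade IV) and 3 (Grade III), with any one criterion sufficient (Protocol 7.1.1). Planned size about 140 (Protocol 9.2).

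**Notation.** Let a, b and c be the numbers of patients with the same related event at Grade III, IV and V. Each patient is counted once, at the highest grade. That counting convention is an assumption, since section 7.1.1 gives none.

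- As written: c ≥ 1, or b ≥ 2, or a ≥ 3.
- With *or higher*: c ≥ 1, or b + c ≥ 2, or a + b + c ≥ 3.

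**Where the two rules differ.** Any pattern that meets the written rule also meets the cumulative one, so they can differ only where the written rule is not met: c = 0, b ≤ 1 and a ≤ 2. There, b + c is at most 1, so the cumulative Grade IV line cannot be met. The cumulative Grade III line needs a + b ≥ 3, which is possible only at a = 2, b = 1. The rules therefore differ at exactly one pattern, (a, b, c) = (2, 1, 0), whatever the trial size.

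**Three patients at Grade III or IV:**

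| Grade III | Grade IV | As written | With *or higher* |
|---|---|---|---|
| 3 | 0 | met | met |
| 2 | 1 | **not met** | met |
| 1 | 2 | met | met |
| 0 | 3 | met | met |

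**Effect of one event worsening by one grade.** Moving a patient from III to IV changes (a, b, c) to (a − 1, b + 1, c). For the written rule to be met before and not after, we need c = 0, b + 1 ≤ 1 and a − 1 ≤ 2. The first two give b = 0 and c = 0, so the rule could have been met before only through a ≥ 3. With a − 1 ≤ 2 this forces a = 3. The single violation is (3, 0, 0) to (2, 1, 0). Moving a patient from IV to V always leaves c ≥ 1, which meets the rule. Under the cumulative rule no worsening lowers any of the sums, so there are no violations.

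**How long the gap lasts.** From (2, 1, 0), the next patient with the same related event gives (3, 1, 0), (2, 2, 0) or (2, 1, 1). All three meet the written rule. A related Grade V event of any kind also meets it. The delay is at most one affected patient: 3/140 = 2.1% becomes 4/140 = 2.9%.

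No probability is attached to the pattern, because the documents give no rate for related Grade III or IV events of one type.

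**The case against.** The strongest reply is that the gap depends on a reading the text does not impose. Section 7.1.1 speaks of patients who experience a Grade III event and does not say that each patient counts only at the highest grade. A patient whose event passed through Grade III on the way to Grade IV has arguably experienced both. A sensible safety reviewer would count a Grade IV case as at least Grade III in any event. The contrast in wording is also weaker than it looks: section 7.1.2 and the SAP summaries use a single cut-off and need cumulative wording, while 7.1.1 is a ladder with a separate line for each grade.

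There are other protections as well. Every patient with a related event of Grade 3 or above must stop study drug (7.1.2). A life-threatening event would ordinarily be serious and reach the sponsor within 24 hours (8.5.1). The sponsor can stop the study at its discretion. Only one pattern is affected, and no estimand, analysis or error rate changes.

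Much of this stands. The cumulative reading is probably what was meant, the scale is small, and the sponsor's power does act at study level. But the cumulative reading is not written down, and it does not cover an event first recorded at Grade IV unless the reviewer chooses to add it. Drug discontinuation acts on patients already affected, and expedited reporting informs the sponsor but sets no threshold. The sponsor's power is discretionary, and a stop under it does not by its terms bring in the Independent Medical Monitor.

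**Conclusion.** The concern holds for the text as written: followed exactly, the rule gives a worse pattern of events a weaker response. It is a minor fault. It affects one pattern (two Grade III, one Grade IV, no Grade V) and delays the trigger by at most one further affected patient. The conclusion assumes that each patient is counted once at the highest grade and that a Grade IV case is not added to the Grade III line. Section 7.1.1 neither requires nor rules out either assumption, and that silence is the defect. Because this is a patient-safety rule with no data monitoring committee behind it, the wording should be corrected.

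**What to change.** In Protocol section 7.1.1, change the Grade III criterion to three patients with the same related event at Grade III *or higher*. That alone closes the gap. Adding the same words to the Grade IV criterion makes the ladder consistent but has no further effect, because any related Grade V event already meets a criterion. Leave the thresholds of 1, 2 and 3 unchanged.

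The cost is a few words of protocol text and, in this one rare pattern, a pause and causality review one patient earlier.
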